10.2.3 Follow-up of serious adverse events

SAEs still ongoing at the EOS visit must be followed up until resolution or stabilization, or until the event outcome is provided, e.g., death.

10.2.4 After the 30-day follow-up period

10.2.4.1 During the PTOP period (if applicable)

All SAEs, regardless of investigator-attributed causal relationship, that occur during the PTOP period must be reported on AE pages in the eCRF and on SAE forms.

10.2.4.2 After the PTOP period

New SAEs occurring after the 30-day FU period, or after the last visit of the PTOP (whichever applies and is the latest) must be reported to the Actelion drug safety department within 24 hours of the investigator's knowledge of the event, **only** if considered causally related to previous exposure to the study treatment by the investigator.

10.2.5 Reporting procedures

All SAEs must be reported by the investigator to the Actelion drug safety department within 24 hours of the investigator's first knowledge of the event.

The MS relapses and associated symptoms are exempt from being reported on an SAE form by the investigator to the Actelion drug safety department with the exceptions described in Section [10.1.6](#).

All SAEs must be recorded on an SAE form, irrespective of the study treatment received by the subject, and whether or not this event is considered by the investigator to be related to study treatment.

The SAE forms must be faxed to the Actelion drug safety department (contact details are provided on the SAE form). The investigator must complete the SAE form in English, and must assess the causal relationship of the event to study treatment.

FU information about a previously reported SAE must also be reported within 24 hours of receiving it. The Actelion drug safety department may contact the investigator to obtain further information.

If the subject is hospitalized in a hospital other than the study site, it is the investigator's responsibility to contact this hospital to obtain all SAE relevant information and documentation.

The reference safety document to assess expectedness of a suspect serious adverse reaction and reported by the sponsor to health authorities, IRBs/IECs and investigators, is the reference safety information section of the IB [[Ponesimod IB](#)].

MS relapses and associated symptoms are commonly seen with the underlying disease and are therefore expected to occur in this subject population. The MS relapses and associated symptoms reported as serious (unless fatal) are waived and will be treated as expected and will therefore not require systematic unblinding or expedited reporting to health authorities, IRBs/IECs, and investigators. However, all MS relapses (irrespective of seriousness) will be collected on the specific relapse pages of the eCRF in the clinical trial database and monitored during the study by the sponsor and by the IDMC.

10.3 Pregnancy

If a woman becomes pregnant while on study treatment, study treatment must be discontinued. The investigator must counsel the subject and discuss the risks of continuing with the pregnancy and the possible effects on the fetus.

10.3.1 Reporting of pregnancy

Irrespective of the treatment received by the subject, any pregnancy occurring during the study including during 30 days following study treatment discontinuation must be reported within 24 hours of the investigator's knowledge of the event.

Pregnancies must be reported on the Actelion Pregnancy form, which is faxed to the Actelion drug safety department (see contact details provided on the Actelion Pregnancy form), and on the AE page in the eCRF.

10.3.2 Follow-up of pregnancy

Any pregnancy must be followed to its conclusion and its outcome must be reported to the Actelion drug safety department.

Any AE associated with the pregnancy occurring during the FU period after study drug discontinuation must be reported on separate AE pages in the eCRF. Any SAE occurring during the pregnancy must be reported on an SAE form as described in Section [10.2.2](#).

10.4 Study safety monitoring

Clinical study safety information (AEs, SAEs, laboratory values, ECGs, vital signs, and project-specific labs/examinations as required) is monitored and reviewed on a continuous basis by the Actelion clinical team (in charge of ensuring subjects' safety as

well as data quality) by periodically monitoring clinical study activities from protocol conception to database closure. In addition, an IDMC is monitoring safety data [see Section 3.8.1].

11 STATISTICAL METHODS

All statistical analyses will be conducted by Actelion or by designated CROs supervised by Actelion.

The Statistical Analysis Plan (SAP) will be approved prior to database lock for the final analyses. The SAP provides the full details of all analyses, data displays, and algorithms to be used for data derivations.

All data will be listed and endpoints will be summarized by appropriate descriptive statistics (tables or figures), typically including:

- Number of non-missing observations, number of missing observations, mean, standard deviation, median, Q1, Q3, minimum and maximum for continuous endpoints;
- Number of non-missing observations, number of missing observations and frequency with percentage per category (percentages based on the number of non-missing observations) for categorical endpoints;
- Number of subjects at risk, cumulative number of events, cumulative number of censored observations and Kaplan-Meier estimates of the survival function for time-to-event endpoints.

Absolute change from baseline is defined as post-baseline value minus baseline value, i.e., a positive sign indicates an increase as compared to baseline.

A percentage (relative) change from baseline is defined as the absolute change from baseline divided by the baseline value (if the baseline value does not = 0) multiplied by 100.

The baseline value for efficacy is defined as the last non-missing value recorded prior to randomization for each endpoint and each subject individually. The baseline value for safety is defined as the last non-missing value recorded prior to first study drug intake for each endpoint and each subject individually.

The EOS is defined as the date on the end-of-study eCRF page. If this date is missing the last recorded visit on the eCRF is considered as the EOS date.

The EOT date is defined as the date of the last dose of study treatment intake.

11.1 Analysis sets

11.1.1 Screened analysis set

The screened analysis set (SCR) includes all subjects who were screened and received a subject number.

11.1.2 Full analysis set

The full analysis set (FAS) includes all randomized subjects who were treated with at least one dose of study treatment and have at least one post-baseline efficacy assessment.

- In order to preserve the randomization, subjects will be evaluated according to the treatment they have been randomized to (which may be different to the treatment they have received) and stratum information used for randomization as recorded in the IVRS system (which may be different to the information available on the eCRF after data validation);
- Unless otherwise stated, all available efficacy data for the primary and secondary endpoints up to the EOS visit will be included in the analysis, regardless of study treatment discontinuation and/or switches to alternative MS treatments.

11.1.3 All-randomized set

The all-randomized set (ARS) includes all subjects that were randomized.

11.1.4 Per-protocol set

The per-protocol set (PPS) comprises all subjects included in the FAS without any major protocol deviations that impact the assessment of the primary/secondary endpoints, occurring prior to or at randomization. Due to the nature of the primary endpoint which is assessed over the entire study period rather than at a fixed timepoint, only the data for a subject collected after a major protocol deviation for subjects developing protocol deviations during the study will be excluded for the PPS analysis.

All reportable protocol deviations will be evaluated before unblinding and classified into the five categories below.

Subjects will be excluded from the PPS if:

- Subject is randomized and did not satisfy certain eligibility criteria;

Data will be excluded for subjects after the occurrence of one of the following criteria:

- Subject developed treatment discontinuation criteria during the study but was not discontinued;
- Subject received the wrong study treatment or incorrect dose;
- Subject took an unauthorized concomitant medication;

- Key study procedures missed or performed out of window (e.g., Randomization code was broken).

Additional details regarding the definition of the reasons for subject/data exclusion from the PPS will be defined in the final SAP.

11.1.5 Safety set

The safety set (SAF) includes all subjects who received at least one dose of study treatment. Subjects will be analyzed based on actual treatment taken.

11.1.6 Other analysis sets

Other analysis datasets will be defined in the SAP (or corresponding SAPs), e.g., PK set, PD set, sub-study sets, and subgroups of interest.

11.1.7 Usage of the analysis sets

The FAS, ARS, and the PPS are used for the analysis of the primary and the secondary endpoints. Results for the primary and secondary efficacy endpoints based on the PPS and ARS will supplement those based on the FAS and assess the robustness of treatment effects.

Other MRI, clinical exploratory endpoints and other exploratory endpoints will be analyzed using the FAS.

All safety data will be analyzed using the SAF.

The usage of other analysis sets will be described in the SAP.

11.2 Variables

Variables are defined only for the primary and secondary endpoints. Variables for exploratory and other endpoints will be defined in the SAP.

11.2.1 Primary efficacy endpoint variable

The primary endpoint is the ARR defined as the number of confirmed relapses per subject-year. All confirmed relapses from randomization up to EOS will be included in the analysis. For the statistical analysis of the ARR, the following variables will be used:

- The subject's number of confirmed relapses up to EOS;
- Length of observation expressed in years, defined as: [EOS date minus date of randomization + 1] divided by 365.25.

For the definition of relapses and confirmed relapses, see Section [6.1.1](#).

11.2.2 Secondary efficacy endpoint variables

There are five secondary efficacy endpoints, which will be analyzed in a hierarchical manner:

- Time to 12-week CDA from baseline up to EOS;
- Time to first confirmed relapse from baseline up to EOS;
- Mean number of CUALs per subject per post-baseline MRI scan up to EOS;
- Longitudinal change over time in fatigue-related symptoms as measured by the symptoms domain of the FSIQ-RMS from baseline up to EOS;
- Longitudinal percent change over time in brain volume from baseline up to EOS.

11.2.2.1 *Time to 12-week CDA from baseline up to EOS*

Time to 12-week CDA from baseline up to EOS is defined as an:

- Increase of at least 1.5 in EDSS for subjects with a baseline EDSS score of 0; or
- Increase of at least 1.0 in EDSS for subjects with a baseline EDSS score of 1.0 to 5.0; or
- Increase of at least 0.5 in EDSS for subjects with a baseline EDSS score ≥ 5.5 ; confirmed after 12 weeks.

Time to first 12-week CDA is defined as the start date of the first 12-week CDA minus date of randomization + 1 in days. For a subject without a 12-week CDA, the censored time to 12-week CDA is defined as:

- [Date of last EDSS assessment up to EOS for subjects without an EDSS increase (as defined above) at their last visit or date of EDSS visit prior to the last visit if there is an increase at the last visit] minus date of randomization + 1.

This will constitute a right-censored observation. Further details of the derivation of this variable will be provided in the SAP.

11.2.2.2 *Time to first confirmed relapse up to EOS*

The time to first confirmed relapse is defined as:

- Date of first confirmed relapse minus date of randomization + 1 in days.

Subjects without any relapses will be censored at the EOS date, and the time is defined as EOS date minus date of randomization + 1 in days.

11.2.2.3 Mean number of CUALs per subject per post-baseline MRI scan up to EOS

The mean number of CUALs [defined in Section 6.1.3] per subject per post-baseline MRI scan up to EOS is calculated per subject as the sum of the lesions at all post-baseline MRI scans up to EOS divided by the number of MRI scans.

11.2.2.4 Longitudinal change over time in fatigue-related symptoms as measured by the symptoms domain of the FSIQ-RMS from baseline up to EOS

The variables required for this endpoint are the visit identifier and the absolute change in the FSIQ-RMS fatigue-related symptoms at each visit defined as the value at each visit up to EOS minus the value at baseline. Additional details for dealing with missing data will be provided in the SAP.

11.2.2.5 Longitudinal percent change over time in brain volume (PCBV) from baseline up to EOS

PCBV will be calculated at each visit using the skull as scaling constraint by performing halfway registration between images from the MRI assessments from baseline up to EOS:

- Percent change from the mean brain surface displacement between the MRI scans (SIENA method).

Further details of the derivation of this variable will be provided in the SAP.

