6.1.2 Secondary efficacy endpoints

There are five secondary efficacy endpoints, which will be analyzed in a hierarchical manner:

- Time to 12-week CDA from baseline up to EOS.

Definition: A 12-week CDA is:

- an increase of at least 1.5 in EDSS for subjects with a baseline EDSS score of 0, or
- an increase of at least 1.0 in EDSS for subjects with a baseline EDSS score of 1.0 to 5.0, or
- an increase of at least 0.5 in EDSS for subjects with a baseline EDSS score ≥ 5.5

which is to be confirmed after 12 weeks.

Baseline EDSS is defined as the last EDSS score recorded during pre-randomization. The initial EDSS increase, meeting the above criteria, is defined as the onset of disability accumulation. All EDSS measurements (with or without relapse, at a scheduled or unscheduled visit) will be used to determine the onset of disability accumulation. However, for the purpose of confirmation, only EDSS measured more than 30 days after the onset of a confirmed relapse will be used. This is to avoid a confirmation of disability accumulation caused by a relapse. In order to confirm that the EDSS increase is persistent, all EDSS measurements between the onset and the 12-week EDSS confirmation (minus visit time-window) need to show an increase in EDSS, meeting the criteria for accumulation of disability as defined above.

- Time to first confirmed relapse up to EOS.

Definition: Relapse definition is given in Section 6.1.1. Date of the first confirmed relapse is defined as the onset date of the first confirmed relapse.

- Mean number of combined unique active lesions (CUALs) per subject per post-baseline MRI scan up to EOS.

Definition: CUALs are new Gd+ T1 lesions plus new or enlarging T2 lesions (without double-counting of lesions).

- Longitudinal change over time in fatigue-related symptoms as measured by the symptoms domain of the FSIQ-RMS from baseline up to EOS.
- Longitudinal percent change over time in brain volume from baseline up to EOS.

Definition: Longitudinal brain volume measurements are derived from MRI scans by using Structural Image Evaluation, using Normalisation, of Atrophy methodology (SIENA) [Smith 2001, Smith 2002].

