7.2 Efficacy assessments

7.2.1 Neurological evaluation

EDSS and FS scores [Kurtzke 1983] are based on a standard neurological examination for assessing neurologic disability and impairment in MS. The seven FS scores are ordinal clinical rating scales ranging from 0 to 5 or 6, assessing visual, brain stem, pyramidal, cerebellar, sensory, bowel and bladder, and cerebral functions while ambulation is an ordinal scale ranging from 0 to 12 assessing walking distance and assistance. The ratings of the individual FS scores are then used, in conjunction with ambulation score, to obtain the EDSS score. EDSS is an ordinal clinical rating scale ranging from 0 (normal neurological examination) to 10 (death due to MS) in half-point increments.

EDSS and FS assessments will be performed at Visit 1 (Screening), Visit 2 (Baseline), Visit 6 (Week 12) and every 12 weeks thereafter until Visit 18 (EOT), Visit 20 (FU), and at any unscheduled visit in the event of relapses (R1, R2, etc.) or other unscheduled visits (U1, U2, etc.). If applicable, EDSS and FS will also be assessed at the corresponding visits in the PTOP (Visits 6A to 18A).

EDSS and FS assessments will only be performed by the efficacy assessor who should preferably maintain this role for a given subject throughout the study [see Section 3.7.3]. The efficacy assessor must not consult prior EDSS/FS scores when performing the current EDSS/FS assessment. In no case will the treating neurologist alter the EDSS/FS score obtained by the efficacy assessor. The examination will be based on the modified neurological examination ‘Neurostatus’ [Appendix 1] using the corresponding scoring documents. The EDSS/FS scoring will be recorded in the eCRF. **NB:** Fatigue, which is an optional part of the ‘Neurostatus’ assessment will not contribute to the Cerebral FS score.

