8.3.1.2 Visit 20 – FU

If a temporary interruption of study treatment lasts more than 30 days and leads to permanent premature discontinuation, Visit 20 (FU) can be combined with the EOT visit.

The FU visit will take place at least 30 days after the last dose of study treatment, but no later than 37 days after last dose of study treatment. The visit includes:

- EDSS/FS.
- MS Relapse.
- FSIQ-RMS. At Visit 20 (FU), the FSIQ-RMS will be completed at home prior to the visit, ideally, during the 7 consecutive days preceding the visit.
- Recording of changes in concomitant medications.
- Body temperature.
- SBP/DBP.
- 12-lead ECG.
- Ophthalmological examination.
- Spirometry.
- Urinalysis.
- Hematology (including lymphocytes*), blood chemistry.
- PK sampling.

- Lymphocyte subsets (only at sites participating in sub-study).
- Serum pregnancy test for WOCBP.
- Recording of AEs and SAEs.

* If a total lymphocyte count $< 0.5 \times 10^9/L$ is observed at FU, an alert will be sent to the principal investigator and the sponsor [see Section 7.3.13.1]. Discontinuation of DMF treatment should be considered in accordance with prescribing information [Tecfidera USPI, Tecfidera SmPC].

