11.3.3.1.2 Analyses

The primary analysis of Time to 12-week CDA will be performed on the FAS using a two-sided stratified log-rank test with stratification factor EDSS category. Kaplan-Meier estimates for the survival functions will be plotted using Kaplan-Meier curves and will be tabulated by 12-week intervals. The treatment effect will be measured by means of a hazard ratio calculated using a Cox’s proportional hazard model with treatment, and baseline EDSS category as covariates.

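### The censoring rule for time to 12-week CDA keeps subjects at risk for at least 77 final days in which no onset can be confirmed, so the tabulated Kaplan-Meier disability rates are too low late in follow-up; the log-rank test and hazard ratio are essentially unaffected

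*Protocol*

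**What the plan says.** Time to 12-week CDA is the first secondary endpoint in the testing hierarchy (Protocol Section 11.3.3).

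- **Event date.** Section 11.2.2.1 dates an event at onset, not at confirmation: "Time to first 12-week CDA is defined as the start date of the first 12-week CDA minus date of randomization + 1 in days".
- **Censoring.** The same section uses the "Date of last EDSS assessment up to EOS for subjects without an EDSS increase (as defined above) at their last visit", or the "date of EDSS visit prior to the last visit if there is an increase at the last visit".
- **Confirmation.** Section 6.1.2 states that "all EDSS measurements between the onset and the 12-week EDSS confirmation (minus visit time-window) need to show an increase in EDSS". An EDSS taken within 30 days of the onset of a confirmed relapse may not serve as confirmation.
- **Schedule.** EDSS is assessed 12-weekly, then at EOT and FU (Section 7.2.1). EOT falls at most 7 days after the last dose (Sections 3.5.2 and 8.2.10). For FU, Section 8.3.1.2 says: "The FU visit will take place at least 30 days after the last dose of study treatment", with 37 days as the upper limit. FU is the EOS visit for treatment completers and for those who stop early without entering the PTOP (Section 3.5.3.3).
- **Reporting.** Kaplan-Meier estimates will be plotted and "will be tabulated by 12-week intervals" (Section 11.3.3.1.2).

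**The concern.** Events are dated at onset, so a day of follow-up belongs in the risk set only if an onset on that day could still be confirmed. The rule carries unworsened subjects up to their last EDSS, past the point where that is possible. They remain in the denominator and cannot enter the numerator.

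The one-visit step-back for worsened subjects works when the last two EDSS visits are about 12 weeks apart. EOT and FU are not. At stake are the absolute disability rates, and the absolute benefit read from them, for the leading secondary endpoint.

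**Working it through.** **The plan's own figure.** Section 11.5.2 gives 120 events for about 90% power at a hazard ratio of 0.55, two-sided 0.05, 1:1 allocation. Schoenfeld: 4 × (1.960 + 1.282)² / (ln 0.55)² = 42.03 / 0.3574 ≈ 118. With 120 events the power is 90.6%. The figure reproduces and is not in question.

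**The schedule.**
- Confirmation interval: 84 − 7 = 77 days.
- Gap from EOT to FU: at least 30 − 7 = 23 days, at most 37 − 1 = 36 days.
- Since 36 < 77, FU cannot confirm an onset first seen at EOT when FU is the last EDSS.
- For any subject censored at the last EDSS, an onset less than 77 days before it cannot be confirmed.
- With FU 30 days after the last dose, 77 days is 77 / (420 + 30) = 17% of follow-up after 60 weeks of treatment and 77 / (1092 + 30) = 7% after 156 weeks.

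**A worked record.** EDSS is 2.0 at baseline, 2.0 at Week 144, 3.0 at EOT (Week 156) and 3.0 at FU. The rise of 1.0 meets the criterion but is not confirmed. FU shows an increase, so censoring moves back one visit, to EOT. The subject counts as event-free up to the day the worsening was recorded. Had FU shown no increase, censoring would have been at FU.

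**Size, by simulation.** Inputs from the protocol:
- placebo 2-year rate 0.30, so hazard −ln(0.7)/2 = 0.178 per year, and hazard ratio 0.55 (Section 11.5.2);
- the 12-weekly visit grid plus EOT and FU;
- closure 60 weeks after the last randomization, with a cap at Week 156;
- 104 weeks of recruitment including the 45-day pre-randomization period, hence 97.6 weeks of randomization (Section 3.5.4).

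Assumptions not in the protocol: exponential persistent onset, uniform accrual, no unscheduled EDSS, and withdrawal of either 0 or 0.15 per year. There were 300,000 subjects per arm. Truth is 1 − exp(−hazard × time); for placebo at Week 144 (2.76 years) this is 1 − exp(−0.492) = 0.389.

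| Kaplan-Meier rate | W48 | W96 | W120 | W144 |
|---|---|---|---|---|
| Placebo, truth | 0.151 | 0.280 | 0.336 | 0.389 |
| Placebo, protocol rule, no withdrawal | 0.151 | 0.267 | 0.312 | 0.343 |
| Placebo, protocol rule, withdrawal 0.15/year | 0.147 | 0.258 | 0.302 | 0.332 |
| Ponesimod, truth | 0.086 | 0.165 | 0.202 | 0.237 |
| Ponesimod, protocol rule, no withdrawal | 0.086 | 0.156 | 0.185 | 0.206 |
| Ponesimod, protocol rule, withdrawal 0.15/year | 0.083 | 0.151 | 0.179 | 0.199 |

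Shortfall on placebo: 0 to 0.4 points at Week 48, 1.3 to 2.2 at Week 96, 4.6 to 5.7 at Week 144. On ponesimod: 0.9 to 1.4 at Week 96, 3.1 to 3.8 at Week 144. The Week 144 difference between arms falls from 38.9 − 23.7 = 15.2 points to 34.3 − 20.6 = 13.7 without withdrawal, or 33.2 − 19.9 = 13.3 with it.

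Per 300 subjects, 5.9 on placebo and 3.8 on ponesimod are censored exactly on an EOT date that already shows the worsening (4.1 and 2.7 with withdrawal). If 20% or 100% of subjects enter the PTOP, placebo at Week 144 is 0.331 or 0.334, so the artefact recurs at the last PTOP visits.

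**The test.** In 600 simulated trials of 300 per arm, the protocol rule was compared with censoring at the last EDSS visit that still has 77 days of later EDSS follow-up. Median hazard ratio was 0.550 against 0.551, and power 88.5% against 88.2%.

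**Which half of the rule causes the bias.** In a further run the protocol rule gave 0.342 for placebo at Week 144 against 0.389. Stepping worsened subjects back to the visit before the onset of the unconfirmed increase gave 0.343, which is no improvement. The bias comes from carrying unworsened subjects to their last EDSS.

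**The case against.** The strongest reply is that nothing confirmatory is touched: the log-rank test and hazard ratio stand, and only descriptive rates move. That is correct. It is also fair that the large gap lies in the tail: in one run only about 35 of 300 placebo and 43 of 300 ponesimod subjects were still at risk at Week 144. Near the plan's own 2-year reference the gap is 1 to 2 points.

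Section 11.3.3.1.3 plans a worst-case analysis that counts unconfirmed accumulations at EOS as confirmed, and the worked record becomes an event there. But that analysis also counts transient worsenings and leaves the main curve as it is. Section 11.2.2.1 leaves further derivation detail to the SAP, yet it states the censoring date itself, so this is a rule fixed badly and not one left open.

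Stronger readings that a reader might infer are not supported:
- *No onset after the last 12-weekly visit can ever be confirmed.* Section 6.1.2 accepts onsets at unscheduled visits. An onset at a Week 146 relapse visit is about 14 weeks before FU and can be confirmed there. In the PTOP, 12-weekly EDSS continues, so an onset at EOT or FU may be confirmed later. The impossibility at EOT and FU is exact only where FU is the EOS visit.
- *The treatment comparison is biased.* Both arms share the schedule, and the simulated hazard ratio does not move.
- *The 24-week CDA rule has the same fault.* The protocol states no separate censoring rule for that exploratory endpoint and leaves its variables to the SAP (Section 11.2).

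**Conclusion.** The point holds as a defect in the absolute rates, not in the test. For subjects whose EOS is FU, the mechanism follows from the protocol's own visit timing and needs no simulation: at least 77 final days at risk with no countable onset, and event-free censoring on the EOT date for those first worsened at EOT and still worse at FU.

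The sizes rest on exponential persistent onset at the planning rates, uniform accrual, withdrawal of 0 to 0.15 per year and no unscheduled EDSS. They are negligible at Week 48, modest at Week 96 and about 5 points at Week 144 on placebo. The change is worth making because these are the rates that Section 11.3.3.1.2 commits to tabulating for the first secondary endpoint.

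**What to change.** In Section 11.2.2.1, replace the bracketed rule with: *date of the last EDSS assessment valid for confirmation up to EOS, minus 12 weeks less the visit window (77 days), and not before randomization*. Apply it to every subject without a 12-week CDA, whether or not an unconfirmed increase is present. Valid for confirmation means more than 30 days after the onset of a confirmed relapse, as in Section 6.1.2.

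No confirmed event is lost, since a confirmed onset lies at least 77 days before the EDSS that confirms it. In simulation this rule gave placebo Week 144 rates of 0.385 to 0.395 across the scenarios tried, against 0.389, including scenarios with onsets first seen at unscheduled visits.

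Two nearby alternatives are not adequate. Changing only the step-back leaves the bias in place. Censoring at the last EDSS visit that is followed by another at least 12 weeks (less the visit window) later overshoots when onsets are first seen at unscheduled visits (0.405 to 0.424), because events can then be dated after the point to which non-events are pulled back.

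The cost is one sentence and a curve that ends about 11 weeks (77 days) earlier, with less nominal follow-up in the tail.
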